## 7.0 ADVERSE EVENTS

## 7.1 Risks of participation

The most common reported adverse events (incidence ≥4.0%) associated with pravastatin are upper respiratory infection (stuffy or runny nose, sneezing, sore throat, or cough), diarrhea, and musculoskeletal pain (aching or stiffness of the body, twitching muscles, etc.). Other adverse events reported in clinical trials (<4%) were angina pectoris, rash, nausea, muscle myalgia, pharyngitis, rhinitis, fatigue, headache, dyspepsia, flatulence, confusion, abdominal distension, influenza, dizziness, allergic reaction, liver failure, and rhabdomyolysis.

Persistent increases in serum transaminases (to more than 3× the ULN) have occurred in approximately 1% of patients who received pravastatin in clinical studies. When drug treatment was interrupted or discontinued in these patients, the transaminase levels usually fell slowly to pretreatment levels. The increases were not associated with jaundice or other clinical signs or symptoms. It is recommended that liver function tests be performed before the initiation of treatment, and thereafter when clinically indicated.

Pravastatin occasionally causes myopathy manifested as muscle pain, tenderness, or weakness with creatine kinase above ten times the ULN. Myopathy sometimes takes the form of rhabdomyolysis with or without acute renal failure secondary to myoglobinuria, and rare fatalities have occurred. The risk of myopathy is increased by high levels of statin activity in plasma. Predisposing factors for myopathy include advanced age (≥65 years), female gender, uncontrolled hypothyroidism, and renal impairment. The risk of myopathy, including rhabdomyolysis, is dose related. The risk of myopathy and rhabdomyolysis is increased by high levels of statin activity in plasma. Pravastatin is metabolized by the cytochrome P450 isoform 3A4 (CYP3A4). Certain drugs which inhibit this metabolic pathway can raise the plasma levels of pravastatin and may increase the risk of myopathy. These include gemfibrozil, cyclosporine, clarithromycin, erythromycin, azithromycin, colchicine, fibrates, niacin, or grapefruit-containing products. Combination of these drugs with pravastatin is contraindicated. If short-term treatment with strong CYP3A4 inhibitors is unavoidable, therapy with pravastatin must be suspended during the course of treatment.

Increases in HbA1c and fasting serum glucose levels have been reported with HMG-CoA reductase inhibitors, including pravastatin.

#### 7.2 Adverse Event Monitoring

Adverse events will be reported in a routine manner at scheduled times during the trial using CTCAE Version 5.0. Certain adverse events must be reported in an expedited manner to allow for optimal monitoring of patient safety and care.

All patients experiencing an adverse event, regardless of its relationship to study drug, will be monitored until:

- The adverse event resolves or the symptoms or signs that constitute the adverse event return to baseline
- Any abnormal laboratory values have returned to baseline
- There is a satisfactory explanation other than the study drug for the changes observed
- Death

## 7.3 **DEFINITIONS**

## 7.3.1 Adverse Event

An adverse event (AE) is any untoward medical occurrence in a patient receiving study treatment and which does not necessarily have a causal relationship with this treatment. An AE can therefore be any unfavorable and unintended sign (including an abnormal laboratory finding), symptom, or disease temporally associated with the use of an experimental intervention, whether or not related to the intervention.

## 7.3.2 Serious Adverse Events

A "serious" adverse event is defined in regulatory terminology as any untoward medical occurrence that:

7.3.2.1 Results in death.

If death results from (progression of) the disease, the disease should be reported as event (SAE) itself.

- 7.3.2.2 Is life-threatening.The patient was at risk of death at the time of the event; it does not refer to an event that hypothetically might have caused death if it were more severe.
- **7.3.2.3** Requires in-patient hospitalization or prolongation of existing hospitalization for  $\ge 24$  hours.
- **7.3.2.4** Results in persistent or significant disability or incapacity.
- 7.3.2.5 Is a congenital anomaly/birth defect
- 7.3.2.6 Is an important medical event
  - Any event that does not meet the above criteria, but that in the judgment of the investigator jeopardizes the patient, may be considered for reporting as a serious adverse event. The event may require medical or surgical intervention to prevent one of the outcomes listed in the definition of "Serious Adverse Event". For example: allergic bronchospasm requiring intensive treatment in an emergency room or at home; convulsions that may not result in hospitalization; development of drug abuse or drug dependency.

## 7.3.3 Unanticipated Problem (UP)

Unanticipated problems include any incident, experience, or outcome that meets all of the following criteria:

- Unexpected (in terms of nature, severity, frequency) given (a) the research procedures that are described in the protocol-related documents, such as the IRB-approved research protocol and informed consent document; and (b) the characteristics of the subject population being studied;
- Related or possibly related to participation in the research (possibly related means there is a reasonable possibility that the incident, experience, or outcome may have been caused by the procedures involved in the research); and
- Suggests that the research places subjects or others at a greater risk of harm (including physical, psychological, economic, or social harm) than was originally anticipated.

## 7.4 Severity of Adverse Events

All non-hematologic adverse events will be graded according to the NCI Common Terminology Criteria for Adverse Events (CTCAE) version 5.0. The CTCAE v5 is available at http://ctep.cancer.gov/reporting/ctc.html

If no CTCAE grading is available, the severity of an AE is graded as follows:

- Mild (grade 1): the event causes discomfort without disruption of normal daily activities.
- Moderate (grade 2): the event causes discomfort that affects normal daily activities.
- Severe (grade 3): the event makes the patient unable to perform normal daily activities or significantly affects his/her clinical status.
- Life-threatening (grade 4): the patient was at risk of death at the time of the event.
- Fatal (grade 5): the event caused death.

## 7.5 Procedures for Recording AEs, SAEs, and Ups

The PI is ultimately responsible for the required reporting of all adverse events. All AEs that occur after the informed consent is signed and baseline measurements (Visit 1) are completed must be recorded on the AE CRF (paper and/or electronic) whether or not related to study agent.

The following data elements are required for AE reporting.

- AE verbatim term
- NCI Common Terminology Criteria for Adverse Events version 5.0 (CTCAE v5.0) AE term (MedDRA lowest level term)
- CTCAE (MedDRA) System Organ Class (SOC)
- Event onset date and event ended date
- Treatment assignment code (TAC) at time of AE onset
- Severity grade
- Attribution to study agent (relatedness)
- Whether or not the event was reported as a SAE
- Whether or not the participant dropped due to the event
- Outcome of the event

## 7.6 Steps to Determine If an Adverse Event Requires Expedited Reporting

Step 1: Identify the type of adverse event using the NCI Common Terminology Criteria for Adverse Events (CTCAE v5).

Step 2: Grade the adverse event using the NCI CTCAE v5.

Step 3: Determine whether the adverse event is related to the protocol therapy Attribution categories are as follows:

- Definite The AE is clearly related to the study treatment.
- Probable The AE is likely related to the study treatment.
- Possible The AE may be related to the study treatment.
- Unlikely related The AE is doubtfully related to the study treatment.
- Unrelated The AE is clearly NOT related to the study treatment.

Note: This includes all events that occur within 30 days of the last dose of protocol treatment. Any event that occurs more than 30 days after the last dose of treatment and is attributed (possibly, probably, or definitely) to the agent(s) must also be reported accordingly.

Step 4: Determine the prior experience of the adverse event.

Expected events are those that have been previously identified as resulting from administration of the agent. An adverse event is considered unexpected, for expedited reporting purposes only, when either the type of event or the severity of the event is not listed in:

- The current known adverse events listed in the Agent Information Section of this protocol
- The drug package insert
- The current Investigator's Brochure

## 7.7 Reporting Requirements for Adverse Events

#### 7.7.1 Expedited Reporting

- The site PI, CSMC protocol PI ([name], CSMC) and medical monitor must be notified by phone within 24 hours of learning of any fatal or serious adverse events, regardless of attribution, occurring during the study or within 30 days of the last administration of the study drug. Include the following information when calling:
  - Date and Time of SAE
  - Date and time of the SAE report
  - Name of reporter
  - Call back phone number
  - Affiliation/Institution conducting study
  - Protocol Number
  - Title of Protocol
  - Description of the SAE, including attribution
- A Serious Adverse Event deemed to be related to the protocol and on-study deaths, including death of a research subject unless the death is expected (e.g. due to disease progression), must be reported to the DSMC within 24 hours for medical monitor ad hoc review between meetings to determine if immediate action is required. Reports may be emailed to the DSMC Admin at [contact].
- Within 48 hours, research study staff must document the SAE using the NCI DCP Serious Adverse Event Form (https://prevention.cancer.gov/clinical-

trials/clinical-trials-management/protocol-information-office/pio-instructionsand-tools/2012-consortia) and email the following people:

- o Site PI
- Protocol PI [name]. [contact] Email: [contact]
- Medical Monitor
   [name]
   [contact]
   Email: [contact]

An unanticipated problem is considered reportable to the Reviewing (CSMC) Institutional Review Board (IRB) and possibly local IRB depending on the institutional/local IRB policies. Research study staff must notify the Site PI, Protocol PI, and the Medical Monitor within 48 hours of learning of any unanticipated problems. Reviewing Institutional Review Board will be notified as soon as possible but no later than 10 calendar days after the Protocol PI becomes aware of any internal or external reportable event. Prompt follow-up reports of the clinical outcome will be sent to the Site PI, Protocol PI, and Medical Monitor.

## 7.7.2 Routine Reporting

All other adverse events- such as those that are expected, or are unlikely or definitely not related to the study participation are to be reported annually as part of regular data submission.

## 8.0 SPECIMEN MANAGEMENT

- Clinical lab testing for blood chemistry, prothrombin time, a lipid panel, hemoglobin A1C, creatine phosphokinase, and AFP will be conducted or coordinated by the clinical laboratories at each institution.
- Research blood specimens and transplant tissue specimens will be collected, processed, and tested as described in the *Laboratory Manual*.

## 9.0 STATISTICAL CONSIDERATIONS

This is a randomized double-blinded, placebo-controlled Phase II trial of statin to evaluate the impact of statin treatment on HCC progression in 130 patients. The primary objective of this study will be to demonstrate that statins will increase TTR. Secondary outcomes will include RFS, overall survival, waitlist drop-off, liver stiffness, liver fat fraction, serum biomarkers, and liver tissue biomarkers.

## 9.1 Randomization/Stratification

Patients will be randomized by the Research Pharmacy at each site. Randomization will be carried out among consented patients meeting the Screening Visit eligibility criteria at each site with a 1:1 ratio for pravastatin and placebo assignment, by blocks based on clinical site and initial HCC treatment type.

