## STUDY SUMMARY

Title	Pravastatin Intervention to Delay Hepatocellular Carcinoma Recurrence
Protocol Number	IIT2017-[name]-StatLv
Phase	Phase II
Methodology	Randomized, double-blinded, placebo-controlled, Phase II trial of statin to increase time to recurrence in patients with liver cirrhosis and initial hepatocellular carcinoma
Study Duration	5 years
Study Center(s)	Cedars-Sinai Medical Center (CSMC), Ronald Reagan UCLA Medical Center (UCLA), Northwestern Memorial Hospital (NWU), UCSF Medical Center (UCSF), Emory University Woodruff Health Sciences Center (EU)
	Primary Objective: To evaluate the effect of a pravastatin intervention versus placebo on the change in time to recurrence (TTR) from baseline to 12 months following treatment initiation.
Objectives	
 
Secondary Objective: To evaluate the effect of a pravastatin intervention versus placebo at 12 months from baseline on:
 
1) Recurrence-free survival
 
2) Overall survival
 
3) Waitlist drop-off
 
4) Change in liver stiffness
 
5) Change in liver fat fraction
 
6) Change in serum biomarkers of monocyte/macrophage and stellate cell activation
 
7) Levels of liver tissue markers related to HCC
 

Number of Subjects	130
Diagnosis and Main Inclusion Criteria	Patients with a confirmed diagnosis of liver cirrhosis (Child-Pugh A or B); current Model for End-Stage Liver Disease (MELD) < 30; Minimum 18 years of age; HCCs must fall within the Milan Criteria or OPTN tumor downstaging criteria; receipt of LRT with verification of adequate response; and patients whose lab results meet the inclusion criteria after the Screening visit blood tests.
Study Product(s), Dose, Route, Regimen	Pravastatin 40 mg and placebo identical in color, consistency, and appearance to pravastatin; oral administration daily (N=65 in each group)
Duration of administration	12 months
Statistical Methodology	Statistical analyses for the primary objective will be conducted on participants who complete the 12 month MRI or CT and blood specimen collection. The distribution of the clinical and demographical covariates, including but not limited to; age, race, smoking status, BMI, and comorbid conditions, will be summarized and compared between the intervention and control groups to assess the adequacy of the randomization. Chance differences between groups will be adjusted for using multiple regression modeling.

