## 9.3.1 Analysis of Primary Endpoint: TTR

The log-rank test will be carried out to compare the distributions of TTR between placebo and pravastatin groups and the Kaplan-Meier estimators will be presented graphically. Cox proportional hazards model will be fitted to the data where the explanatory variable of interest is the indicator of treatment allocation adjusting for clinical and demographic baseline covariates, including sex. Patients who did not experience HCC recurrence, or receive a liver transplant and are still alive at the end of the study will be right censored. Patients who are transplanted or die before HCC recurrence will be treated as a competing risk. A competing risk model for TTR will be used to estimate the cumulative incidence of TTR using time to transplant or death as a competing risk. The proportional hazards assumption will be tested graphically and analytically, and model diagnostics such as martingale and Schoenfeld residuals will be conducted to assess model adequacy. Violation of the proportional hazards assumption will be addressed by use of time-dependent covariates or extended Cox models. The possibility of collinearity among the explanatory variables will be reduced after careful assessment of the correlation matrix and condition index. Automatic variable selection methods in a multivariable Cox proportional hazards model such as stepwise, backward, and forward will be used as a guideline to identify sets of important predictors and a more rigorous approach based on a 4-step procedure outlined in Collett (2003) will be employed (55). Power. Preliminary data indicate that the 12-month RFS is between 57% and 78% in patients with: 1) Child Pugh A or B cirrhosis, 2) small HCCs (typically meeting Milan criteria) 3) liver directed therapy (typically RFA or resection), and 4) no other interventions (27, 56-59). Therefore, we will assume that the 12-month RFS in the control group is 65%. Assuming a common cumulative incidence of the competing risk events at 12 months of 20% (10% due to liver transplant and 10% due to death), a 42-month accrual time and 15-month follow up time, and 10% drop out, data from 47 patients per group achieve 80% power to detect a hazard ratio of 0.45 using a two-sided log-rank test with a 0.1 level of significance. This is equivalent to detecting a decrease in the 12-month cumulative incidence of disease recurrence from 35% in the control group to 18% in the treatment group, which is clinically meaningful. The choice of a type I error rate of 0.1 is appropriate for a randomized phase II trial since this can serve as a randomized screening design for a nondefinitive comparison of statin vs placebo (reference: Mandrekar and Sargent (2010)). We further assumed that TTR and time to death or transplant are independent and exponentially distributed. Statistical power was based on the formulas in Machin et al. (2008) and Pintilie (2006) and were carried out using PASS version 13 (60, 61).

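### Randomisation is blocked by site and initial HCC treatment type, but the primary log-rank test is unstratified and the Cox model neither names these factors nor protects them from variable selection

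*Combined protocol and SAP*

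**What the plan says.** - **Randomisation.** Section 9.1 assigns patients 1:1 "by blocks based on clinical site and initial HCC treatment type". Block size and the treatment-type categories are not given.
- **Primary test.** Section 9.3.1: "The log-rank test will be carried out to compare the distributions of TTR between placebo and pravastatin groups". No strata are mentioned. The power statement uses the same kind of test, "using a two-sided log-rank test with a 0.1 level of significance".
- **Cox model.** Section 9.3.1 estimates the treatment effect "adjusting for clinical and demographic baseline covariates, including sex". Sex is the only covariate named.
- **Choice of covariates.** Section 9.3.1: "Automatic variable selection methods in a multivariable Cox proportional hazards model such as stepwise, backward, and forward will be used as a guideline", alongside a stepwise procedure taken from a textbook. No covariate is declared exempt from selection.
- **Study Summary.** The covariates for baseline comparison, and for adjustment where chance differences appear, are an open list, "including but not limited to; age, race, smoking status, BMI, and comorbid conditions". Neither site nor HCC treatment type is on it.

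**The concern.** Blocking within site and treatment type forces the arms to be nearly balanced on both factors. If a factor predicts recurrence, that balance reduces the true variability of the treatment comparison. A log-rank test that ignores the factor does not count this reduction. Its standard error is then a little too large, its real type I error falls below the nominal 0.10, and some power is lost.

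The Cox model does not clearly make up for this. Initial treatment type could be counted as a clinical covariate, but nothing requires it and selection could remove it. Site is not naturally a clinical or demographic covariate.

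Two things are at stake: a few points of power in a trial expecting roughly 33 to 38 events, and a choice left open that should be settled in advance. Section 5.3 lists the study biostatisticians among those who are unblinded, so strata or covariates chosen late would be open to criticism.

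**Working it through.** **1. The plan's own power figure.** Section 9.3.1 states that "data from 47 patients per group achieve 80% power to detect a hazard ratio of 0.45", with recurrence falling "from 35% in the control group to 18% in the treatment group, which is clinically meaningful".

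- Inputs from 9.3.1: 12-month cumulative incidence of recurrence 35% (control) and of competing events 20%; 42 months of accrual plus 15 of follow-up; 10% drop-out; two-sided 0.10.
- Total hazard in controls: −ln(1 − 0.35 − 0.20)/12 = 0.0665 per month. Recurrence share: 0.0665 × 35/55 = 0.0423. Competing share: 0.0665 × 20/55 = 0.0242.
- Treated recurrence hazard: 0.45 × 0.0423 = 0.0191. The 12-month incidence is 0.0191/(0.0191 + 0.0242) × (1 − exp(−12 × 0.0433)) = 0.18, as stated.
- With 10% annual drop-out as a hazard, 47 per arm give 37.8 expected events.
- Schoenfeld power: Φ(√37.8/2 × |ln 0.45| − 1.645) = Φ(2.455 − 1.645) = 0.79.

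The stated 80% reproduces for an unstratified log-rank test.

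**2. What ignoring the blocking factors does.** The documents give no prognostic effect for either factor, so a range was simulated. Assumed: five sites (from the Study Schema; 9.2 says three), two treatment types, permuted blocks of four within site by type, and the effect sizes in the tables. Site SD is on the log-hazard scale. All tests were run on the same simulated trials.

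*94 analysed patients, 42 + 15 months, 5,000 trials per setting (Monte Carlo standard error about 0.6 points for power, 0.004 for type I error).* The type I columns are under no treatment effect. Power, in %, is at hazard ratio (HR) 0.45.

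| Type HR, site SD | Type I, unstratified | Type I, by type | Power, unstratified | By type (change) | By site × type (change) |
|---|---|---|---|---|---|
| 1, 0 | 0.107 | 0.108 | 78.1 | 76.8 (−1.3) | 71.2 (−6.9) |
| 1.5, 0.2 | 0.097 | 0.102 | 74.9 | 74.6 (−0.3) | 70.3 (−4.6) |
| 2, 0.2 | 0.094 | 0.101 | 73.1 | 74.8 (+1.7) | 69.6 (−3.5) |
| 3, 0.4 | 0.074 | 0.085 | 65.6 | 69.9 (+4.3) | 67.0 (+1.4) |

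*130 randomised, 12-month window as in the section 2.3 definition of TTR, about 33 events, 6,000 trials per setting.*

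| Type HR, site SD | Power, unstratified | By type (change) | By site × type (change) |
|---|---|---|---|
| 1, 0 | 72.7 | 72.4 (−0.3) | 71.3 (−1.4) |
| 2, 0.2 | 71.4 | 72.9 (+1.5) | 71.6 (+0.2) |
| 3, 0.4 | 68.2 | 70.3 (+2.1) | 70.8 (+2.6) |

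In the last row the unstratified type I error was 0.079.

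**3. Why not every cell.** Two types by five sites make 10 cells, so 94/10 ≈ 9 patients and 37.8/10 ≈ 4 events per cell. With three types (15 cells, 94 patients, 6,000 trials), full stratification lowered power in every setting:

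| Type HR, site SD | Power, unstratified | By type (change) | By site × type (change) |
|---|---|---|---|
| 1, 0 | 77.4 | 76.2 (−1.2) | 68.2 (−9.2) |
| 1.5, 0.2 | 75.2 | 73.9 (−1.3) | 67.1 (−8.1) |
| 2, 0.2 | 74.4 | 73.6 (−0.8) | 66.3 (−8.1) |
| 3, 0.4 | 67.7 | 70.1 (+2.4) | 65.1 (−2.6) |

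**4. Covariate adjustment instead of strata.** A Cox Wald test with site and type both forced in (94 patients, 42 + 15 months, two types) had power 78.0%, 77.0%, 76.6% and 73.8% over the four settings. Its type I error was 0.11 to 0.12, so part of that gain is not real. This favours a stratified log-rank as the test and the Cox model for estimation.

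**The case against.** The strongest reply is that nothing is invalid. The unstratified test keeps its size or falls below it. The power calculation assumed the same test and reproduces. The open covariate list can include treatment type. Site may be a blocking factor only because each site's pharmacy randomises its own patients, and the documents give no evidence that either factor predicts recurrence. In a phase II screening design at 0.10, a gain of 0 to 4 points is small.

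Most of this stands, and it limits the size of the point. It does not close the gap: the plan still does not say how the factors enter, and selection could remove treatment type from the Cox model.

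Three stronger readings are tempting and are not supported:

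- A reader might infer that the primary test certainly is conservative and loses power. That needs prognostic factors. At type HR 1.5 to 2 the unstratified type I error was 0.094 to 0.097 in the first table, close to nominal.
- A reader might take the fall from 78.1% to 65.6% in that table as the cost of ignoring the strata. Most of it comes from the heterogeneity itself. Stratifying by type recovers 4.3 points.
- A reader might infer that the analysis should mirror the randomisation cell by cell. With 94 patients that usually costs more than it returns.

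**Conclusion.** The point holds as one of efficiency and pre-specification. The primary analysis as written ignores both randomisation factors. Compared with a log-rank stratified by treatment type, and assuming two types, five sites and blocks of four, the unstratified test gives up about 0 to 2 points of power for modest to moderate prognostic effects. For strong effects (type HR 3, site SD 0.4) it gives up about 2 to 4 points, with type I error about 0.07 to 0.08 instead of 0.10. If the factors are not prognostic there is no loss, and type I error is not materially inflated in any case.

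The textual gap is certain. The size is not: the number of types, the block size and the strength of both factors are assumptions.

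**What to change.** In section 9.3.1:

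1. Make the primary test a two-sided log-rank stratified by initial HCC treatment type. Define the categories, and pool small ones by a written rule before unblinding. As the study biostatisticians are already unblinded, the rule itself belongs in the plan.
2. Stratify the Cox model by treatment type and force site in as a covariate. Exempt both from stepwise or other selection.
3. Keep the unstratified log-rank as a sensitivity analysis.
4. Do not stratify on every site-by-type cell. With 94 analysed patients this can cost about 3 to 7 points with two types, and more with three.

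The cost is a change of wording, with no new data or patients. The downside is about 1 power point if treatment type is not prognostic (1.3 points in the worst run). With three types, a cost of about that size also remained at modest to moderate effects.
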